363.72 HEMORRHAGIC CHOROIDAL DETACH 423 HEMOPERICARDIUM 430 SUBARACHNOID HEMORRHAGE 568.81 HEMOPERITONEUM (NONTRAUMATIC) 719.1 HEMARTHROSIS SITE UNSPECIFIED 719.13 HEMARTHROSIS INVOLVING FOREARM 719.16 HEMARTHROSIS INVOLVING LOWER LEG 719.18 HEMARTHROSIS INVOLVING OTHER SPECIFIED SITES 852 SUBARACHNOID HEMORRHAGE FOLLOWING INJURY WITHOUT MENTION OF OPEN INTRACRANIAL WOUND 852.02 SUBARACHNOID HEMORRHAGE FOLLOWING INJURY WITHOUT OPEN INTRACRANIAL WOUND WITH BRIEF (LESS THAN ONE HOUR) LOSS OF CONSCIOUSNESS 852.04 SUBARACHNOID HEMORRHAGE FOLLOWING INJURY WITHOUT OPEN INTRACRANIAL WOUND WITH PROLONGED (MORE THAN 24 HOURS) LOSS OF CONSCIOUSNESS AND RETURN TO PRE-EXISTING CONSCIOUS LEVEL 852.1 SUBARACHNOID HEMORRHAGE FOLLOWING INJURY WITH OPEN INTRACRANIAL WOUND 852.13 SUBARACHNOID HEMORRHAGE FOLLOWING INJURY WITH OPEN INTRACRANIAL WOUND WITH MODERATE (1-24 HOURS) LOSS OF CONSCIOUSNESS 852.14 SUBARACHNOID HEMORRHAGE FOLLOWING INJURY WITH OPEN INTRACRANIAL WOUND WITH PROLONGED (MORE THAN 24 HOURS) LOSS OF CONSCIOUSNESS AND RETURN TO PRE-EXISTING CONSCIOUS LEVEL 852.16 SUBARACHNOID HEMORRHAGE FOLLOWING INJURY WITH OPEN INTRACRANIAL WOUND WITH LOSS OF CONSCIOUSNESS OF UNSPECIFIED DURATION 852.2 SUBDURAL HEMORRHAGE FOLLOWING INJURY WITHOUT MENTION OF OPEN INTRACRANIAL WOUND 852.21 SUBDURAL HEMORRHAGE FOLLOWING INJURY WITHOUT OPEN INTRACRANIAL WOUND WITH NO LOSS OF CONSCIOUSNESS 852.23 SUBDURAL HEMORRHAGE FOLLOWING INJURY WITHOUT OPEN INTRACRANIAL WOUND WITH MODERATE (1-24 HOURS) LOSS OF CONSCIOUSNESS 852.24 SUBDURAL HEMORRHAGE FOLLOWING INJURY WITHOUT OPEN INTRACRANIAL WOUND WITH PROLONGED (MORE THAN 24 HOURS) LOSS OF CONSCIOUSNESS AND RETURN TO PRE-EXISTING CONSCIOUS LEVEL 852.26 SUBDURAL HEMORRHAGE FOLLOWING INJURY WITHOUT OPEN INTRACRANIAL WOUND WITH LOSS OF CONSCIOUSNESS OF UNSPECIFIED DURATION 852.29 SUBDURAL HEMORRHAGE FOLLOWING INJURY WITHOUT OPEN INTRACRANIAL WOUND WITH CONCUSSION UNSPECIFIED 852.36 SUBDURAL HEMORRHAGE FOLLOWING INJURY WITH OPEN INTRACRANIAL WOUND WITH LOSS OF CONSCIOUSNESS OF UNSPECIFIED DURATION 852.39 SUBDURAL HEMORRHAGE FOLLOWING INJURY WITH OPEN INTRACRANIAL WOUND WITH CONCUSSION UNSPECIFIED 852.4 EXTRADURAL HEMORRHAGE FOLLOWING INJURY WITHOUT MENTION OF OPEN INTRACRANIAL WOUND 852 4 EXTRADURAL HEMORRHAGE FOLLOWING INJURY WITHOUT OPEN INTRACRANIAL WOUND WITH STATE OF CONSCIOUSNESS UNSPECIFIED 852.41 EXTRADURAL HEMORRHAGE FOLLOWING INJURY WITHOUT OPEN INTRACRANIAL WOUND WITH NO LOSS OF CONSCIOUSNESS 852.44 EXTRADURAL HEMORRHAGE FOLLOWING INJURY WITHOUT OPEN INTRACRANIAL WOUND WITH PROLONGED (MORE THAN 24 HOURS) LOSS OF CONSCIOUSNESS AND RETURN TO PRE-EXISTING CONSCIOUS LEVEL EXTRADURAL HEMORRHAGE FOLLOWING INJURY WITHOUT OPEN INTRACRANIAL WOUND WITH LOSS OF CONSCIOUSNESS OF UNSPECIFIED DURATION 852.46 EXTRADURAL HEMORRHAGE FOLLOWING INJURY WITH OPEN INTRACRANIAL WOUND 852.5 852.5 EXTRADURAL HEMORRHAGE FOLLOWING INJURY WITH OPEN INTRACRANIAL WOUND WITH STATE OF CONSCIOUSNESS UNSPECIFIED 852.51 EXTRADURAL HEMORRHAGE FOLLOWING INJURY WITH OPEN INTRACRANIAL WOUND WITH NO LOSS OF CONSCIOUSNESS 852.52 EXTRADURAL HEMORRHAGE FOLLOWING INJURY WITH OPEN INTRACRANIAL WOUND WITH BRIEF (LESS THAN ONE HOUR) LOSS OF CONSCIOUSNESS EXTRADURAL HEMORRHAGE FOLLOWING INJURY WITH OPEN INTRACRANIAL WOUND WITH MODERATE (1-24 HOURS) LOSS OF CONSCIOUSNESS 852 53 852.55 EXTRADURAL HEMORRHAGE FOLLOWING INJURY WITH OPEN INTRACRANIAL WOUND WITH PROLONGED (MORE THAN 24 HOURS) LOSS OF CONSCIOUSNESS WITHOUT RETURN TO PRE-EXISTING CONSCIOUS LEVEL EXTRADURAL HEMORRHAGE FOLLOWING INJURY WITH OPEN INTRACRANIAL WOUND WITH LOSS OF CONSCIOUSNESS OF UNSPECIFIED DURATION 852.56 852.59 EXTRADURAL HEMORRHAGE FOLLOWING INJURY WITH OPEN INTRACRANIAL WOUND WITH CONCUSSION UNSPECIFIED 853 OTHER AND UNSPECIFIED INTRACRANIAL HEMORRHAGE FOLLOWING INJURY WITHOUT MENTION OF OPEN INTRACRANIAL WOUND OTHER AND UNSPECIFIED INTRACRANIAL HEMORRHAGE FOLLOWING INJURY WITHOUT OPEN INTRACRANIAL WOUND WITH BRIEF (LESS THAN ONE HOUR) LOSS OF CONSCIOUSNESS 853 02 853.06 OTHER AND UNSPECIFIED INTRACRANIAL HEMORRHAGE FOLLOWING INJURY WITHOUT OPEN INTRACRANIAL WOUND WITH LOSS OF CONSCIOUSNESS OF UNSPECIFIED 853.09 OTHER AND UNSPECIFIED INTRACRANIAL HEMORRHAGE FOLLOWING INJURY WITHOUT OPEN INTRACRANIAL WOUND WITH CONCUSSION UNSPECIFIED 853 1 OTHER AND UNSPECIFIED INTRACRANIAL HEMORRHAGE FOLLOWING INJURY WITH OPEN INTRACRANIAL WOUND WITH STATE OF CONSCIOUSNESS UNSPECIFIED 853.16 OTHER AND UNSPECIFIED INTRACRANIAL HEMORRHAGE FOLLOWING INJURY WITH OPEN INTRACRANIAL WOUND WITH LOSS OF CONSCIOUSNESS OF UNSPECIFIED DURATION 853.19 OTHER AND UNSPECIFIED INTRACRANIAL HEMORRHAGE FOLLOWING INJURY WITH OPEN INTRACRANIAL WOUND WITH CONCUSSION UNSPECIFIED 866.01 HEMATOMA OF KIDNEY WITHOUT RUPTURE OF CAPSULE WITHOUT OPEN WOUND INTO CAVITY HEMATOMA OF KIDNEY WITHOUT RUPTURE OF CAPSULE WITH OPEN WOUND INTO CAVITY 866 11 LACERATION OF KIDNEY WITH OPEN WOUND INTO CAVIT 866 12 The occurrence of Inpatient Confinement with the following attributes: Procedure Code (Any Confinement Position) is any of: { "99.05", "99.03", "99.04", "99.06" 99 05 TRANSFUSION OF PLATELETS 99.03 OTHER TRANSFUSION OF WHOLE BLOOD 99.04 TRANSFUSION OF PACKED CELLS

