
99.06 TRANSFUSION OF COAGULATION FACTORS

AND

ICD-9 Dx

- 455.1 INTERNAL THROMBOSED HEMORRHOIDS
- 455.7 UNSPECIFIED THROMBOSED HEMORRHOIDS
- 455.8 UNSPECIFIED HEMORRHOIDS WITH OTHER COMPLICATION
- 455.9 RESIDUAL HEMORRHOIDAL SKIN TAGS
- 459 HEMORRHAGE UNSPECIFIED
- 530.1 ESOPHAGITIS
- 530.1 ESOPHAGITIS UNSPECIFIED
- 530.13 EOSINOPHILIC ESOPHAGITIS
- 530.19 OTHER ESOPHAGITIS
- 530.7 GASTROESOPHAGEAL LACERATION-HEMORRHAGE SYNDROME
- 530.82 ESOPHAGEAL HEMORRHAGE
- 531 ACUTE GASTRIC ULCER WITH HEMORRHAGE
- 531.01 ACUTE GASTRIC ULCER WITH HEMORRHAGE WITH OBSTRUCTION
- 531.2 ACUTE GASTRIC ULCER WITH HEMORRHAGE AND PERFORATION WITHOUT OBSTRUCTION
- 531.21 ACUTE GASTRIC ULCER WITH HEMORRHAGE AND PERFORATION WITH OBSTRUCTION
- 531.3 ACUTE GASTRIC ULCER WITHOUT MENTION OF HEMORRHAGE OR PERFORATION
- 531.4 CHRONIC OR UNSPECIFIED GASTRIC ULCER WITH HEMORRHAGE WITHOUT OBSTRUCTION
- 531.5 CHRONIC OR UNSPECIFIED GASTRIC ULCER WITH PERFORATION
- 531.6 CHRONIC OR UNSPECIFIED GASTRIC ULCER WITH HEMORRHAGE AND PERFORATION WITHOUT OBSTRUCTION
- 531.61 CHRONIC OR UNSPECIFIED GASTRIC ULCER WITH HEMORRHAGE AND PERFORATION WITH OBSTRUCTION
- 531.7 CHRONIC GASTRIC ULCER WITHOUT MENTION OF HEMORRHAGE OR PERFORATION
- 531.9 GASTRIC ULCER UNSPECIFIED AS ACUTE OR CHRONIC WITHOUT MENTION OF HEMORRHAGE OR PERFORATION
- 532 ACUTE DUODENAL ULCER WITH HEMORRHAGE WITHOUT OBSTRUCTION
- 532.01 ACUTE DUODENAL ULCER WITH HEMORRHAGE WITH OBSTRUCTION
- 532.1 ACUTE DUODENAL ULCER WITH PERFORATION
- 532.3 ACUTE DUODENAL ULCER WITHOUT MENTION OF HEMORRHAGE OR PERFORATION
- 532.4 CHRONIC OR UNSPECIFIED DUODENAL ULCER WITH HEMORRHAGE
- 532.41 CHRONIC OR UNSPECIFIED DUODENAL ULCER WITH HEMORRHAGE WITH OBSTRUCTION
- 532.5 CHRONIC OR UNSPECIFIED DUODENAL ULCER WITH PERFORATION
- 532.9 DUODENAL ULCER UNSPECIFIED AS ACUTE OR CHRONIC WITHOUT MENTION OF HEMORRHAGE OR PERFORATION
- 533.1 ACUTE PEPTIC ULCER OF UNSPECIFIED SITE WITH PERFORATION
- 533.2 ACUTE PEPTIC ULCER OF UNSPECIFIED SITE WITH HEMORRHAGE AND PERFORATION
- 533.21 ACUTE PEPTIC ULCER OF UNSPECIFIED SITE WITH HEMORRHAGE AND PERFORATION WITH OBSTRUCTION
- 533.4 CHRONIC OR UNSPECIFIED PEPTIC ULCER OF UNSPECIFIED SITE WITH HEMORRHAGE WITHOUT OBSTRUCTION
- 533.41 CHRONIC OR UNSPECIFIED PEPTIC ULCER OF UNSPECIFIED SITE WITH HEMORRHAGE WITH OBSTRUCTION
- 533.5 CHRONIC OR UNSPECIFIED PEPTIC ULCER OF UNSPECIFIED SITE WITH PERFORATION
- 533.6 CHRONIC OR UNSPECIFIED PEPTIC ULCER OF UNSPECIFIED SITE WITH HEMORRHAGE AND PERFORATION

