- 784.7 EPISTAXIS 784.8 HEMORRHAGE FROM THROAT 786.3 HEMOPTYSIS 786.39 OTHER HEMOPTYSIS 280 IRON DEFICIENCY ANEMIA SECONDARY TO BLOOD LOSS (CHRONIC) 285.1 ACUTE POSTHEMORRHAGIC ANEMIA 455.2 INTERNAL HEMORRHOIDS WITH OTHER COMPLICATION 455.4 EXTERNAL THROMBOSED HEMORRHOIDS 455.5 EXTERNAL HEMORRHOIDS WITH OTHER COMPLICATION 455.6 UNSPECIFIED HEMORRHOIDS WITHOUT COMPLICATION 456 ESOPHAGEAL VARICES WITH BLEEDING 456.2 ESOPHAGEAL VARICES IN DISEASES CLASSIFIED ELSEWHERE WITH BLEEDING 530.11 REFLUX ESOPHAGITIS 530.12 ACUTE ESOPHAGITIS 531 ACUTE GASTRIC ULCER WITH HEMORRHAGE WITHOUT OBSTRUCTION 531.1 ACUTE GASTRIC ULCER WITH PERFORATION ACUTE GASTRIC ULCER WITH HEMORRHAGE AND PERFORATION 531.2 5314 CHRONIC OR UNSPECIFIED GASTRIC ULCER WITH HEMORRHAGE 531.41 CHRONIC OR UNSPECIFIED GASTRIC ULCER WITH HEMORRHAGE WITH OBSTRUCTION 531.6 CHRONIC OR UNSPECIFIED GASTRIC ULCER WITH HEMORRHAGE AND PERFORATION 532 ACUTE DUODENAL ULCER WITH HEMORRHAGE 532.2 ACUTE DUODENAL ULCER WITH HEMORRHAGE AND PERFORATION 532.2 ACUTE DUODENAL ULCER WITH HEMORRHAGE AND PERFORATION WITHOUT OBSTRUCTION 532.21 ACUTE DUODENAL ULCER WITH HEMORRHAGE AND PERFORATION WITH OBSTRUCTION 532.4 CHRONIC OR UNSPECIFIED DUODENAL ULCER WITH HEMORRHAGE WITHOUT OBSTRUCTION 532.6 CHRONIC OR UNSPECIFIED DUODENAL ULCER WITH HEMORRHAGE AND PERFORATION 532.6 CHRONIC OR UNSPECIFIED DUODENAL ULCER WITH HEMORRHAGE AND PERFORATION WITHOUT OBSTRUCTION 532.61 CHRONIC OR UNSPECIFIED DUODENAL ULCER WITH HEMORRHAGE AND PERFORATION WITH OBSTRUCTION 532.7 CHRONIC DUODENAL ULCER WITHOUT MENTION OF HEMORRHAGE OR PERFORATION 533 ACUTE PEPTIC ULCER OF UNSPECIFIED SITE WITH HEMORRHAGE 533 ACUTE PEPTIC ULCER OF UNSPECIFIED SITE WITH HEMORRHAGE WITHOUT OBSTRUCTION 533.01 ACUTE PEPTIC ULCER OF UNSPECIFIED SITE WITH HEMORRHAGE WITH OBSTRUCTION 533.2 ACUTE PEPTIC ULCER OF UNSPECIFIED SITE WITH HEMORRHAGE AND PERFORATION WITHOUT OBSTRUCTION 533.3 ACUTE PEPTIC ULCER OF UNSPECIFIED SITE WITHOUT MENTION OF HEMORRHAGE AND PERFORATION 533.4 CHRONIC OR UNSPECIFIED PEPTIC ULCER OF UNSPECIFIED SITE WITH HEMORRHAGE 533.6 CHRONIC OR UNSPECIFIED PEPTIC ULCER OF UNSPECIFIED SITE WITH HEMORRHAGE AND PERFORATION WITHOUT OBSTRUCTION 533.61 CHRONIC OR UNSPECIFIED PEPTIC ULCER OF UNSPECIFIED SITE WITH HEMORRHAGE AND PERFORATION WITH OBSTRUCTION 533.7 CHRONIC PEPTIC ULCER OF UNSPECIFIED SITE WITHOUT MENTION OF HEMORRHAGE OR PERFORATION 534 ACUTE GASTROJEJUNAL ULCER WITH HEMORRHAGE WITHOUT OBSTRUCTION 534.01 ACUTE GASTROJEJUNAL ULCER WITH HEMORRHAGE WITH OBSTRUCTION 534.1 ACUTE GASTROJEJUNAL ULCER WITH PERFORATION 534.2 ACUTE GASTROJEJUNAL ULCER WITH HEMORRHAGE AND PERFORATION WITHOUT OBSTRUCTION 534.3 ACUTE GASTROJEJUNAL ULCER WITHOUT MENTION OF HEMORRHAGE OR PERFORATION 534.41 CHRONIC OR UNSPECIFIED GASTROJEJUNAL ULCER WITH HEMORRHAGE WITH OBSTRUCTION 534.5 CHRONIC OR UNSPECIFIED GASTROJEJUNAL ULCER WITH PERFORATION 534.61 CHRONIC OR UNSPECIFIED GASTROJEJUNAL ULCER WITH HEMORRHAGE AND PERFORATION WITH OBSTRUCTION 534.7 CHRONIC GASTROJEJUNAL ULCER WITHOUT MENTION OF HEMORRHAGE OR PERFORATION 535 ACUTE GASTRITIS (WITHOUT HEMORRHAGE) 535.01 ACUTE GASTRITIS WITH HEMORRHAGE 535.1 ATROPHIC GASTRITIS (WITHOUT HEMORRHAGE) 535.2 GASTRIC MUCOSAL HYPERTROPHY (WITHOUT HEMORRHAGE) 535.21 GASTRIC MUCOSAL HYPERTROPHY WITH HEMORRHAGE 535.3 ALCOHOLIC GASTRITIS (WITHOUT HEMORRHAGE) 535.41 OTHER SPECIFIED GASTRITIS WITH HEMORRHAGE 535.5 UNSPECIFIED GASTRITIS AND GASTRODUODENITIS (WITHOUT HEMORRHAGE) 535.6 DUODENITIS (WITHOUT HEMORRHAGE)

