- 537.83 ANGIODYSPLASIA OF STOMACH AND DUODENUM WITH HEMORRHAGE
- 562 DIVERTICULOSIS OF SMALL INTESTINE (WITHOUT HEMORRHAGE)
- 562.02 DIVERTICULOSIS OF SMALL INTESTINE WITH HEMORRHAGE
- 562.1 DIVERTICULOSIS OF COLON (WITHOUT HEMORRHAGE)

562.13 DIVERTICULITIS OF COLON WITH HEMORRHAGE

- 569.3 HEMORRHAGE OF RECTUM AND ANUS
- 578 HEMATEMESIS
- 578.9 HEMORRHAGE OF GASTROINTESTINAL TRACT UNSPECIFIED
- 593.81 VASCULAR DISORDERS OF KIDNEY
- 599.7 HEMATURIA UNSPECIFIED
- 623.6 VAGINAL HEMATOMA
- 626.6 METRORRHAGIA
- 786.3 HEMOPTYSIS UNSPECIFIED
- 786.31 ACUTE IDIOPATHIC PULMONARY HEMORRHAGE IN INFANTS

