S06.4X2A	Epidural hemorrhage with loss of consciousness of 31 minutes to 59 minutes, initial encounter
S06.4X2D	Epidural hemorrhage with loss of consciousness of 31 minutes to 59 minutes, subsequent encounter
S06.4X3D	Epidural hemorrhage with loss of consciousness of 1 hour to 5 hours 59 minutes, subsequent encounter
S06.4X3S	Epidural hemorrhage with loss of consciousness of 1 hour to 5 hours 59 minutes, sequela
S06.4X4D	Epidural hemorrhage with loss of consciousness of 6 hours to 24 hours, subsequent encounter
S06 4X4S	Epidural hemorrhage with loss of consciousness of 6 hours to 24 hours, sequela

S06.4X4S Epidural hemorrhage with loss of consciousness of 6 hours to 24 hours, sequela

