S06.4X5 Epidural hemorrhage with loss of consciousness greater than 24 hours with return to pre-existing conscious level S06.4X5A Epidural hemorrhage with loss of consciousness greater than 24 hours with return to pre-existing conscious level, initial encounter S06.4X6 Epidural hemorrhage with loss of consciousness greater than 24 hours without return to pre-existing conscious level with patient surviving S06 4X6A Epidural hemorrhage with loss of consciousness greater than 24 hours without return to pre-existing conscious level with patient surviving, initial encounter S06 4X6S Epidural hemorrhage with loss of consciousness greater than 24 hours without return to pre-existing conscious level with patient surviving, seguela S06.4X8 Epidural hemorrhage with loss of consciousness of any duration with death due to other causes prior to regaining consciousness S06.4X8A Epidural hemorrhage with loss of consciousness of any duration with death due to other causes prior to regaining consciousness, initial encounter S06.4X9D Epidural hemorrhage with loss of consciousness of unspecified duration, subsequent encounter S06.4X9S Epidural hemorrhage with loss of consciousness of unspecified duration, seguela S06.5X0A Traumatic subdural hemorrhage without loss of consciousness initial encounter S06.5X0D Traumatic subdural hemorrhage without loss of consciousness, subsequent encounter S06.5X0S Traumatic subdural hemorrhage without loss of consciousness, sequela S06.5X1 Traumatic subdural hemorrhage with loss of consciousness of 30 minutes or less S06.5X1A Traumatic subdural hemorrhage with loss of consciousness of 30 minutes or less, initial encounter S06.5X1D Traumatic subdural hemorrhage with loss of consciousness of 30 minutes or less, subsequent encounter S06.5X1S Traumatic subdural hemorrhage with loss of consciousness of 30 minutes or less, seguela S06.5X2D Traumatic subdural hemorrhage with loss of consciousness of 31 minutes to 59 minutes, subsequent encounter S06 5X2S Traumatic subdural hemorrhage with loss of consciousness of 31 minutes to 59 minutes, seguela S06.5X3 Traumatic subdural hemorrhage with loss of consciousness of 1 hour to 5 hours 59 minutes S06 5X4 Traumatic subdural hemorrhage with loss of consciousness of 6 hours to 24 hours S06.5X4A Traumatic subdural hemorrhage with loss of consciousness of 6 hours to 24 hours, initial encounter S06.5X4D Traumatic subdural hemorrhage with loss of consciousness of 6 hours to 24 hours, subsequent encounter S06.5X5D Traumatic subdural hemorrhage with loss of consciousness greater than 24 hours with return to pre-existing conscious level, subsequent encounter S06 5X6 Traumatic subdural hemorrhage with loss of consciousness greater than 24 hours without return to pre-existing conscious level with patient surviving S06 5X7 Traumatic subdural hemorrhage with loss of consciousness of any duration with death due to brain injury before regaining consciousness S06.5X7A Traumatic subdural hemorrhage with loss of consciousness of any duration with death due to brain injury before regaining consciousness, initial encounter S06 5X8A Traumatic subdural hemorrhage with loss of consciousness of any duration with death due to other cause before regaining consciousness, initial encounter S06 5X9 Traumatic subdural hemorrhage with loss of consciousness of unspecified duration S06.6 Traumatic subarachnoid hemorrhage S06.6X0S Traumatic subarachnoid hemorrhage without loss of consciousness, seguela S06.6X1D Traumatic subarachnoid hemorrhage with loss of consciousness of 30 minutes or less, subsequent encounter S06.6X2 Traumatic subarachnoid hemorrhage with loss of consciousness of 31 minutes to 59 minutes S06.6X2A Traumatic subarachnoid hemorrhage with loss of consciousness of 31 minutes to 59 minutes, initial encounter S06.6X2S Traumatic subarachnoid hemorrhage with loss of consciousness of 31 minutes to 59 minutes, seguela S06.6X3 Traumatic subarachnoid hemorrhage with loss of consciousness of 1 hour to 5 hours 59 minutes S06.6X3A Traumatic subarachnoid hemorrhage with loss of consciousness of 1 hour to 5 hours 59 minutes, initial encounter S06.6X3S Traumatic subarachnoid hemorrhage with loss of consciousness of 1 hour to 5 hours 59 minutes, seguela S06.6X4D Traumatic subarachnoid hemorrhage with loss of consciousness of 6 hours to 24 hours, subsequent encounter S06 6X5A Traumatic subarachnoid hemorrhage with loss of consciousness greater than 24 hours with return to pre-existing conscious level, initial encounter S06.6X5D Traumatic subarachnoid hemorrhage with loss of consciousness greater than 24 hours with return to pre-existing conscious level, subsequent encounter S06 6X6D Traumatic subarachnoid hemorrhage with loss of consciousness greater than 24 hours without return to pre-existing conscious level with patient surviving, subsequent encounter S06.6X7A Traumatic subarachnoid hemorrhage with loss of consciousness of any duration with death due to brain injury prior to regaining consciousness, initial encounter S06.6X8 Traumatic subarachnoid hemorrhage with loss of consciousness of any duration with death due to other cause prior to regaining consciousness S06 6X9 Traumatic subarachnoid hemorrhage with loss of consciousness of unspecified duration S06 6X9A Traumatic subarachnoid hemorrhage with loss of consciousness of unspecified duration, initial encounter S06 6X9D Traumatic subarachnoid hemorrhage with loss of consciousness of unspecified duration, subsequent encounter S26.00 Unspecified injury of heart with hemopericardium S26.00XA Unspecified injury of heart with hemopericardium, initial encounter S26.00XD Unspecified injury of heart with hemopericardium, subsequent encounter S26.00XS Unspecified injury of heart with hemopericardium, sequela S26.01XD Contusion of heart with hemopericardium, subsequent encounter S26.01XS Contusion of heart with hemopericardium, sequela S26.02 Laceration of heart with hemopericardium S26.020D Mild laceration of heart with hemopericardium, subsequent encounter S26.020S Mild laceration of heart with hemopericardium, sequela S26.021 Moderate laceration of heart with hemopericardium S26.021A Moderate laceration of heart with hemopericardium, initial encounter S26.022A Major laceration of heart with hemopericardium, initial encounter S26.022S Major laceration of heart with hemopericardium, sequela S26.09XA Other injury of heart with hemopericardium, initial encounter

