Inpatient, Any Diagnosis: ICD-9 Codes 280.0 - IRON DEFICIENCY ANEMIA SECONDARY TO BLOOD LOSS (CHRONIC) 455.7 - UNSPECIFIED THROMBOSED HEMORRHOIDS 459.0 - HEMORRHAGE UNSPECIFIED 530.10 - ESOPHAGITIS UNSPECIFIED 530.13 - EOSINOPHILIC ESOPHAGITIS 531.0 - ACUTE GASTRIC ULCER WITH HEMORRHAGE 531.1 - ACUTE GASTRIC UI CER WITH PERFORATION 531.2 - ACUTE GASTRIC ULCER WITH HEMORRHAGE AND PERFORATION 531.20 - ACUTE GASTRIC ULCER WITH HEMORRHAGE AND PERFORATION WITHOUT OBSTRUCTION 531.3 - ACUTE GASTRIC ULCER WITHOUT MENTION OF HEMORRHAGE OR PERFORATION 531.4 - CHRONIC OR UNSPECIFIED GASTRIC ULCER WITH HEMORRHAGE 531.6 - CHRONIC OR UNSPECIFIED GASTRIC ULCER WITH HEMORRHAGE AND PERFORATION 531.61 - CHRONIC OR UNSPECIFIED GASTRIC ULCER WITH HEMORRHAGE AND PERFORATION WITH OBSTRUCTION 531.9 - GASTRIC ULCER UNSPECIFIED AS ACUTE OR CHRONIC WITHOUT MENTION OF HEMORRHAGE OR PERFORATION 532.0 - ACUTE DUODENAL ULCER WITH HEMORRHAGE 532.00 - ACUTE DUODENAL ULCER WITH HEMORRHAGE WITHOUT OBSTRUCTION 532.01 - ACUTE DUODENAL ULCER WITH HEMORRHAGE WITH OBSTRUCTION 532.2 - ACUTE DUODENAL ULCER WITH HEMORRHAGE AND PERFORATION 532.20 - ACUTE DUODENAL ULCER WITH HEMORRHAGE AND PERFORATION WITHOUT OBSTRUCTION 532.3 - ACUTE DUODENAL ULCER WITHOUT MENTION OF HEMORRHAGE OR PERFORATION 532.4 - CHRONIC OR UNSPECIFIED DUODENAL ULCER WITH HEMORRHAGE 532.41 - CHRONIC OR UNSPECIFIED DUODENAL ULCER WITH HEMORRHAGE WITH OBSTRUCTION 532.5 - CHRONIC OR UNSPECIFIED DUODENAL ULCER WITH PERFORATION 532.61 - CHRONIC OR UNSPECIFIED DUODENAL ULCER WITH HEMORRHAGE AND PERFORATION WITH OBSTRUCTION 533.0 - ACUTE PEPTIC ULCER OF UNSPECIFIED SITE WITH HEMORRHAGE 533.00 - ACUTE PEPTIC ULCER OF UNSPECIFIED SITE WITH HEMORRHAGE WITHOUT OBSTRUCTION 533.01 - ACUTE PEPTIC ULCER OF UNSPECIFIED SITE WITH HEMORRHAGE WITH OBSTRUCTION 533.1 - ACUTE PEPTIC ULCER OF UNSPECIFIED SITE WITH PERFORATION 533.2 - ACUTE PEPTIC ULCER OF UNSPECIFIED SITE WITH HEMORRHAGE AND PERFORATION 533.20 - ACUTE PEPTIC ULCER OF UNSPECIFIED SITE WITH HEMORRHAGE AND PERFORATION WITHOUT OBSTRUCTION 533.3 - ACUTE PEPTIC ULCER OF UNSPECIFIED SITE WITHOUT MENTION OF HEMORRHAGE AND PERFORATION 533.6 - CHRONIC OR UNSPECIFIED PEPTIC ULCER OF UNSPECIFIED SITE WITH HEMORRHAGE AND PERFORATION 533.60 - CHRONIC OR UNSPECIFIED PEPTIC ULCER OF UNSPECIFIED SITE WITH HEMORRHAGE AND PERFORATION WITHOUT OBSTRUCTION 533.7 - CHRONIC PEPTIC ULCER OF UNSPECIFIED SITE WITHOUT MENTION OF HEMORRHAGE OR PERFORATION 534.00 - ACUTE GASTROJEJUNAL ULCER WITH HEMORRHAGE WITHOUT OBSTRUCTION 534.01 - ACUTE GASTROJEJUNAL ULCER WITH HEMORRHAGE WITH OBSTRUCTION 534.20 - ACUTE GASTROJEJUNAL ULCER WITH HEMORRHAGE AND PERFORATION WITHOUT OBSTRUCTION 534.3 - ACUTE GASTROJEJUNAL ULCER WITHOUT MENTION OF HEMORRHAGE OR PERFORATION 534.40 - CHRONIC OR UNSPECIFIED GASTROJEJUNAL ULCER WITH HEMORRHAGE WITHOUT OBSTRUCTION 534.41 - CHRONIC OR UNSPECIFIED GASTROJEJUNAL ULCER WITH HEMORRHAGE WITH OBSTRUCTION 534.61 - CHRONIC OR UNSPECIFIED GASTROJEJUNAL ULCER WITH HEMORRHAGE AND PERFORATION WITH OBSTRUCTION 534.7 - CHRONIC GASTROJEJUNAL ULCER WITHOUT MENTION OF HEMORRHAGE OR PERFORATION 534.9 - GASTROJEJUNAL ULCER UNSPECIFIED AS ACUTE OR CHRONIC WITHOUT MENTION OF HEMORRHAGE OR PERFORATION 535.00 - ACUTE GASTRITIS (WITHOUT HEMORRHAGE) 535.01 - ACUTE GASTRITIS WITH HEMORRHAGE 535.10 - ATROPHIC GASTRITIS (WITHOUT HEMORRHAGE) 535.20 - GASTRIC MUCOSAL HYPERTROPHY (WITHOUT HEMORRHAGE)

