
535.21 - GASTRIC MUCOSAL HYPERTROPHY WITH HEMORRHAGE 535.31 - ALCOHOLIC GASTRITIS WITH HEMORRHAGE 535.40 - OTHER SPECIFIED GASTRITIS (WITHOUT HEMORRHAGE) 535.41 - OTHER SPECIFIED GASTRITIS WITH HEMORRHAGE 562.00 - DIVERTICULOSIS OF SMALL INTESTINE (WITHOUT HEMORRHAGE) 562.01 - DIVERTICULITIS OF SMALL INTESTINE (WITHOUT HEMORRHAGE) 562.03 - DIVERTICULITIS OF SMALL INTESTINE WITH HEMORRHAGE 562.11 - DIVERTICULITIS OF COLON (WITHOUT HEMORRHAGE) 562.13 - DIVERTICULITIS OF COLON WITH HEMORRHAGE 569.85 - ANGIODYSPLASIA OF INTESTINE WITH HEMORRHAGE 578.0 - HEMATEMESIS 578.1 - BLOOD IN STOOL 578.9 - HEMORRHAGE OF GASTROINTESTINAL TRACT UNSPECIFIED 593.81 - VASCULAR DISORDERS OF KIDNEY 599.70 - HEMATURIA UNSPECIFIED 599.71 - GROSS HEMATURIA 623.6 - VAGINAL HEMATOMA 626.6 - METRORRHAGIA 784.7 - FPISTAXIS 784.8 - HEMORRHAGE FROM THROAT 786.31 - ACUTE IDIOPATHIC PULMONARY HEMORRHAGE IN INFANTS 285.1 - ACUTE POSTHEMORRHAGIC ANEMIA 455.1 - INTERNAL THROMBOSED HEMORRHOIDS 455.2 - INTERNAL HEMORRHOIDS WITH OTHER COMPLICATION 455.4 - EXTERNAL THROMBOSED HEMORRHOIDS 455.5 - EXTERNAL HEMORRHOIDS WITH OTHER COMPLICATION 455.6 - UNSPECIFIED HEMORRHOIDS WITHOUT COMPLICATION 455.8 - UNSPECIFIED HEMORRHOIDS WITH OTHER COMPLICATION 455.9 - RESIDUAL HEMORRHOIDAL SKIN TAGS 456.0 - ESOPHAGEAL VARICES WITH BLEEDING 456.20 - ESOPHAGEAL VARICES IN DISEASES CLASSIFIED ELSEWHERE WITH BLEEDING 530.1 - ESOPHAGITIS 530.11 - REFLUX ESOPHAGITIS 530.12 - ACUTE ESOPHAGITIS 530.19 - OTHER ESOPHAGITIS 530.7 - GASTROESOPHAGEAL LACERATION-HEMORRHAGE SYNDROME 530.82 - ESOPHAGEAL HEMORRHAGE 531.00 - ACUTE GASTRIC ULCER WITH HEMORRHAGE WITHOUT OBSTRUCTION 531.01 - ACUTE GASTRIC ULCER WITH HEMORRHAGE WITH OBSTRUCTION 531.21 - ACUTE GASTRIC ULCER WITH HEMORRHAGE AND PERFORATION WITH OBSTRUCTION 531.40 - CHRONIC OR UNSPECIFIED GASTRIC ULCER WITH HEMORRHAGE WITHOUT OBSTRUCTION 531.41 - CHRONIC OR UNSPECIFIED GASTRIC ULCER WITH HEMORRHAGE WITH OBSTRUCTION 531.5 - CHRONIC OR UNSPECIFIED GASTRIC ULCER WITH PERFORATION 531.60 - CHRONIC OR UNSPECIFIED GASTRIC ULCER WITH HEMORRHAGE AND PERFORATION WITHOUT OBSTRUCTION 531.7 - CHRONIC GASTRIC ULCER WITHOUT MENTION OF HEMORRHAGE OR PERFORATION 532.1 - ACUTE DUODENAL ULCER WITH PERFORATION 532.21 - ACUTE DUODENAL ULCER WITH HEMORRHAGE AND PERFORATION WITH OBSTRUCTION 532.40 - CHRONIC OR UNSPECIFIED DUODENAL ULCER WITH HEMORRHAGE WITHOUT OBSTRUCTION

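### The Major Bleeding code sheet prints shortened ICD-9 codes that conflict with the CRNM sheet and lists aftercare and late-effect injury codes as new bleeds, so it is mis-specified and may mis-capture major bleeding.

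*Combined protocol and SAP*

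**What the plan says.** Section 6.3.1 makes major plus CRNM bleeding the primary outcome, lists each separately as a secondary outcome, and sends the reader to the Appendix for definitions. Appendix A defines major bleeding by the Major Bleeding sheet: an inpatient code in any diagnosis position, with a transfusion code also required for non-critical sites. CRNM bleeding uses its own sheet, also inpatient and in any position, with no transfusion requirement. The active-bleeding exclusion reuses both sheets over [-180, 0]. Under Section 6.3.2 follow-up ends at the first outcome.

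The ICD-9 transfusion block of the Major Bleeding sheet has rows such as "459 HEMORRHAGE UNSPECIFIED", "578 HEMATEMESIS" and "280 IRON DEFICIENCY ANEMIA SECONDARY TO BLOOD LOSS (CHRONIC". For two of these labels the CRNM sheet has "578.0 - HEMATEMESIS" and "280.0 - IRON DEFICIENCY ANEMIA SECONDARY TO BLOOD LOSS (CHRONIC". The critical-site block, which needs no transfusion code, includes "423 HEMOPERICARDIUM".

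The ICD-10 critical-site list includes "S06.5X0S Traumatic subdural hemorrhage without loss of consciousness, sequela" and a row labelled "Epidural hemorrhage with loss of consciousness of 31 minutes to 59 minutes, subsequent encounter". Nothing limits the outcome to initial encounters.

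**The concern.** The sheet is the working specification for three parts of the study, so a programmer who follows it as printed has to decide what a shortened code means. If codes are matched exactly, a claim carrying 578.0 does not match 578, and a transfused hematemesis admission drops out of major bleeding. If codes are matched by prefix, a short code may take in neighbouring diagnoses. The plan does not say which rule applies.

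The ICD-10 issue is separate. By their own labels, subsequent-encounter and sequela codes describe follow-up or late effects of an earlier injury. Counting them as events could turn a bleed from before treatment into an on-treatment major bleed. No row on the ICD-9 list is labelled this way, so the two coding eras are not defined alike.

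**Working it through.** No figure in the plan is built row by row from these sheets, so there is none to reproduce. The feasibility event totals in Section 7 (2,226, 2,570 and 17,135) are for the composite and are not split by code or component.

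**ICD-9, transfusion block.** I matched each row to the CRNM sheet by identical label. Of 130 rows, 93 agree and 37 do not (37/130 = 28%). In all 37 the only difference is lost trailing zeros. Examples:

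| Label (abridged) | Major Bleeding | CRNM |
|---|---|---|
| Hemorrhage, unspecified | 459 | 459.0 |
| Hematemesis | 578 | 578.0 |
| Blood-loss iron deficiency anemia | 280 | 280.0 |
| Bleeding esophageal varices | 456 | 456.0 |
| Acute gastric ulcer, hemorrhage, no obstruction | 531 | 531.00 |
| Hematuria, unspecified | 599.7 | 599.70 |

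Fourteen of the 37 rows shrink to three digits, giving ten distinct codes: 280, 456, 459, 531, 532, 533, 534, 535, 562 and 578. Eighteen codes in the block are each printed against two labels, among them 530.1 and 531. In the critical-site block 432 also carries two labels.

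This is not PDF damage. On the same sheet, decimals that do not end in zero survive (531.01, 531.21), and so do zeros in alphanumeric codes (H43.10). The CRNM sheet keeps its zeros throughout.

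**What the 37 rows can cost.** Seven 535 rows, two 562 rows and unspecified esophagitis are not bleeds by label, which makes 10. Four more (531.0, 532.0, 533.0, 534.0) are parent headings whose sub-codes have their own rows. That leaves 37 - 10 - 4 = 23 rows naming a bleed that exact matching on the printed strings could drop from major bleeding. Each of the 37 has its full code on the CRNM sheet without a transfusion requirement, so a dropped admission would still count as CRNM and still enter the composite and the exclusion.

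Under prefix matching, 531-535, 562 and 578 add little, because the sheet already lists most of their sub-codes. That leaves 10 - 7 = 3 short codes (280, 456, 459) that could draw in unlisted neighbours, and only for transfused admissions.

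**Critical-site rows.** Neither 423 nor 432 has a CRNM counterpart, so a miss or an over-capture there goes straight into the composite.

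**How many patients fall under ICD-9.** The documents do not date the change of coding system, so this is an assumption with a range. In the matched calendar-year table of Appendix B, rivaroxaban entrants in 2012-2014 number 9,590 + 29,838 = 39,428 of 184,107 (21%), where 9,590 = 897 + 2,413 + 6,280. Adding all of 2015 gives 39,428 + 37,079 = 76,507 (42%).

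**ICD-10.** Codes printed with a final D or S number 80: 40 D and 40 S, or S37 36 + S06 32 + S26 12. Another 16 rows have such labels but lost their code in extraction. A false event needs three things together: such a code on an inpatient claim in follow-up, no listed inpatient code in [-180, 0], and no earlier outcome. An injury more than 180 days before entry, or one treated only outside hospital, meets the second condition.

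**The case against.** The strongest reply is that print is not execution. Lost trailing zeros are what numeric spreadsheet cells produce. Two labels under one short code imply that two distinct codes lay behind the print, and the transfusion query on the same sheet shows its codes as quoted text. The platform may well have run the full codes. This stands: it leaves both the direction and the existence of any miscount unknown. It does not rescue the sheet as a specification.

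It is also fair that 14 of the 37 rows cost little or nothing, that the CRNM sheet shields the composite for all 37, and that hemopericardium, with no counterpart, cannot itself show the conflict. That 423 was shortened is inferred from the pattern elsewhere. Its part of the PDF shows other extraction damage, such as missing decimal points.

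On the injury codes, a subsequent-encounter code at a later admission may follow a genuine on-treatment bleed. The outcome row cites a published Medicare study from which the list may have been inherited, which cannot be checked here. That argues for keeping the D codes in a sensitivity analysis. It does not justify counting sequela codes as new bleeds.

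A reader might infer that major bleeding has been mis-captured in both coding eras, or that 37 kinds of bleeding are lost. The documents support neither, because they show neither the strings run nor the matching rule. The further inference that 423 would absorb all pericardial disease, or 280 all iron-deficiency anemia, rests on ICD-9 structure that the documents do not give.

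**Conclusion.** The Major Bleeding sheet is mis-specified and may mis-capture major bleeding. The conflict covers 37 of 130 transfusion-block rows, 23 of which name a bleed that exact matching on the printed strings could drop from major bleeding. For the 37 rows the stake is the separate major and CRNM outcomes. Through truncation the primary composite is exposed only at critical-site rows such as 423 and 432. At least 80 aftercare or late-effect injury codes can also add false events to the composite, but the conditions are narrow and this is probably rare.

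The size in events cannot be computed, the direction is unknown, and nothing shows that any error would differ by drug. The conclusion assumes that the printed sheet is the operative definition, as Section 6.3.1 and Appendix A say. It should be corrected before the comparative analyses, whose Section 13 is still blank.

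**What to change.** Store ICD-9 codes as text and restore the full codes, from the CRNM sheet where the label is shared and from the source code list for critical-site rows. State exact matching. Confirm which strings the platform executed, and re-run the exclusion and counts if they were the shortened ones. Restoring zeros does not settle whether the ten rows without a bleeding label belong under major bleeding.

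Remove the S and D injury codes from the outcome definition and add a sensitivity analysis that keeps the D codes. Both may stay in the baseline exclusion, where a record of an earlier injury is what is wanted.

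The cost is a code-sheet correction, a possible re-run and slightly fewer trauma-coded events. No new data are needed.
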